2 RATIONALE AND JUSTIFICATION FOR THE STUDY AND THE STUDY DESIGN

2.1 Rationale for the Study Design

This open-label, pilot study is designed to explore the initial efficacy and safety of PRN1008 in PV and to enable the accurate design of pivotal randomized clinical trials which are to follow. An open-label design was chosen for several reasons: PV does not spontaneously remit so there is no placebo effect to account for; clinicians need to know when to use rescue corticosteroids, if necessary, in a timely manner; and lastly, the pilot nature of the investigation itself is best explored in an open-label fashion.

Because of the ability to guide individualized dosing with BTK occupancy measurement, the use of which has been validated in a naturally occurring canine pemphigus study, this assay was used to supplement the clinical response assessments in making dose-adjustments in **Part A**. More than 95% of patients in **Part A** (20/21) had adequate BTK occupancies (mean 86% pre dose at steady-state). In **Part B**, the clinical efficacy of the 400 mg qd dose is being explored to see if lower BTK occupancies will still equate to clinical efficacy. For this reason, clinical response alone, and not BTK occupancies, is recommended to guide dose adjustment in **Part B**.

Given the efficacy seen in this pemphigus study to date at varied clinical severities, and the updated, supporting, chronic, GLP toxicology ([Section 1.3](#)), there is clinical equipoise to study PRN1008 monotherapy (or with low dose CS) in patients with mild-to-severe (baseline PDAI 8-60), corticosteroid-naïve or relapsing PV, with close observation and appropriate corticosteroid rescue protocols.

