2.2 Study Design

This is a Phase 2, open-label, pilot cohort study to evaluate the safety, clinical activity, pharmacodynamics, and pharmacodynamics of PRN1008 in patients with newly diagnosed or relapsing PV. An open-label design was chosen for several reasons: PV does not spontaneously remit so there is no placebo effect to account for; clinicians need to know when to use rescue CSs, if necessary, in a timely manner; and lastly, the pilot nature of the investigation itself is best explored in an open-label fashion.

Up to 28 days before enrollment in the study, patients will be required to sign an informed consent form, after which screening assessments will be carried out. Patients must fulfill all entry criteria to be enrolled into the study. Patients who fail to meet the entry criteria may be rescreened at the discretion of the Investigator. Up to 25 male or female patients with newly diagnosed (i.e., naïve to an effective induction treatment regimen) or relapsing, biopsy-proven, mild or moderate PV patients (Pemphigus Disease Activity Index [PDAI] 8 to 45) to enrolled into each parts of the study.

In Part A, the initial dosing was 400 mg twice daily (bid). The duration of study therapy was 12 weeks starting on Day 1 and ending on study Day 84 (total duration of individual subject participation is 28 weeks), with follow-up visits (off-treatment) until Week 29.

In Part B, the initial dosing is 400 mg once daily (qd), with intra-patient dose escalation to 400 mg bid allowed at or after the Week 3 visit for insufficient clinical response (and then again to 600 mg bid if necessary at or after the Week 5 visit). The duration of study therapy is 24 weeks starting on Day 1 and ending on study Day 169, with a follow-up visit (off-treatment) on Day 197 (Week 29). The total duration of individual subject participation is approximately 32 weeks.

Dose Escalation Rules Part B

Current Dose	Inadequate Clinical Response* Dose-Escalation Rules
400 mg qd	Increase to 400 mg bid (allowed at Week 3 visit or later)**
400 mg bid	Increase to 600 mg bid (allowed at Week 5 visit or later)**
600 mg bid	No dose increase possible.

* Investigator discretion: Generally, clinical response is shown by some improvement seen in first 2 weeks with CDA achieved by the Week 5 visit

** Unless tolerability issues preclude dose-escalation

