5.4 Efficacy Analyses

The mITT population will be used for all efficacy analyses. For analyses at a particular study drug dose, all patients who received that dose at least once will be included. In addition, for selected analyses, where specified, the Completer and PP population will be used.

The descriptive statistics will be done by dose level and overall for all study visits, unless specified otherwise. All binomial confidence intervals for efficacy analyses will use the Exact (Clopper-Pearson) method. Patient data listings will be listed by starting dose, patient, dose level and study visit.

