5.4.2.4 CS Dose on the Day Before Each Visit

For each patient on the day before each scheduled visit, dosage level of CS dose in mg/day and mg/kg/day will be summarized using summary statistics by dose level and overall. Types of CS other than prednis(ol)one are converted to dose-equivalent prednis(ol)one (see Section 5.4.2.3).

For Screening and Week 1/Day 1 visits, however, the CS dose is set as the day of, rather than the day before.

If a patient did not report any CS, then the dosage level is set as 0. If a subject is terminated prior to a visit, then this subject is not included in the calculation for visit.

The same table will be repeated for: 1) patients achieved at least one CDA and 2) to included patients achieved at least one.

A listing of the CS dose in mg/day and mg/kg/day will be listed with the CDA and CR response at each visit. Change from Baseline in PDAI ABSIS, ABQOL and TABQOL Scores

Quantitative assessment of patient response and disease progression will be determined using the following scores at visits specified in the Schedule of assessments (Table 1):

- 1) Pemphigus Disease Area Index (PDAI) score – Total Activity Score
- 2) Pemphigus Disease Area Index (PDAI) score – Total Damage Score
- 3) Autoimmune Bullous Skin Disorder Intensity Score (ABSIS) score
- 4) Autoimmune Bullous Disease Quality of Life (ABQOL) score
- 5) Treatment of Autoimmune Bullous Disease Quality of Life (TABQOL) score

The PDAI questionnaire has two components including activity and damage. The activity component consists of skin, scalp and mucosa parts and the damage component consists of skin and scalp parts. Actual values, change from screening, percent change from screening, change from baseline and percent change from baseline in PDAI total activity, total damage scores will be summarized by dose level and overall, respectively.

The PDAI activity or damage total scores per body part will be calculated as the sum of the scores on that body part as follows. PDAI total activity and total damage scores will be calculated as follows:

- PDAI total activity score = Total skin activity + Total scalp activity + Total mucosa activity
- PDAI total damage score = Total skin damage + Total scalp damage

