The ABSIS questionnaire has three components, including skin involvement, oral involvement and (oral) severity. The ABSIS scores will be calculated separately for each component. The ABSIS total activity score and total ABSIS score will also be calculated as follows:

- Skin involvement total score = sum of (%BSA * Weighting factor for each skin involvement area)
- Oral involvement total score = sum of (score from each oral part)
- (Oral) Severity total score = sum of (Level * Factor of discomfort for each food item)
- ABSIS total activity score = Skin involvement total score + Oral involvement total score
- Total ABSIS score = Skin involvement total score + Oral involvement total score + Severity total score

Actual values and change from baseline in ABSIS skin involvement total score, ABSIS oral involvement total score and ABSIS total activity score will be summarized for all patients, and for the two sub-groups:

- baseline oral involvement total score = 0 vs. >0
- baseline skin involvement score = 0 vs >0.

When calculating skin involvement total score, if %BSA = 0, then skin involvement score component is 0. If %BSA > 0, then weighting factor needs to be considered, and if weighting factor is missing in this circumstance, then the skin involvement total score and ABSIS total score are considered missing.

The ABQOL and TABQOL questionnaires both contains 17 questions with numerical scores. The ABQOL and TABQOL scores will be calculated as the sum of scores from each question. Actual values and change from baseline in ABQOL and TABQOL scores will also be summarized by dose level and overall in a table. If individual scores are missing, then the total scores are set as missing.

PDAI, ABSIS, ABQOL and TABQOL scores and sub-scores (for PDAI and ABSIS) by patient and visit will be presented in separate listings.

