5.4.2.5 Change from Baseline in Simple Nutritional Appetite Questionnaire (SNAQ) score

Simple Nutritional Appetite Questionnaire (SNAQ) contains 4 questions with numerical scores and is assessed at visits specified in the Schedule of assessments (Table 1). The SNAQ score will be calculated as the sum of scores from each question. The SNAQ score ranges from 4 to 20. If individual scores are missing, then the total score is set as missing.

Actual values and change from baseline in SNAQ score at each visit will be summarized by dose level and overall.

The SNAQ score will be presented in a listing by patient and visit.

5.4.2.1 *Change from Baseline and Percent Change from Baseline in Total Anti-DSG, Anti-DSG 1 and Anti-DSG 3*

The Anti-DSG 1 and Anti-DSG 3 results are measured at visits specified in the Schedule of assessments (Table 1). Total Anti-DSG is the sum of Anti-DSG 1 and Anti-DSG3, where at least one of Anti-DSG 1 or 3 is positive per Section 5.1.3, i.e. Anti-DSG 1 \geq 14 and/or Anti-DSG 3 \geq 9.

Actual result, change from baseline and percent change from baseline in Total Anti-DSG, positive Anti-DSG1, i.e. \geq 14, and positive Anti-DSG 3, i.e. \geq 9, at each visit will be summarized by dose level and overall. The same descriptive statistics will be produced by baseline Anti-DSG value (\geq 100 units vs. $<$ 100 unit).

The Total Anti-DSG, Anti-DSG 1 and Anti-DSG 3 values will be presented in a listing by patient and visit.

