Mean (SD)	x.xx (x.xxx)	x.xx (x.xxx)	x.xx (x.xxx)	x.xx (x.xxx)
Median	x.xx	x.xx	x.xx	x.xx
Min, Max	x.x, x.x	x.x, x.x	x.x, x.x	x.x, x.x
WEEK 3 DAY 15				
n	x	x	x	x
Mean (SD)	x.xx (x.xxx)	x.xx (x.xxx)	x.xx (x.xxx)	x.xx (x.xxx)
Median	x.xx	x.xx	x.xx	x.xx
Min, Max	x.x, x.x	x.x, x.x	x.x, x.x	x.x, x.x
WEEK 3 DAY 15 – CHANGE FROM SCREENED				
n	x	x	x	x
Mean (SD)	x.xx (x.xxx)	x.xx (x.xxx)	x.xx (x.xxx)	x.xx (x.xxx)
Median	x.xx	x.xx	x.xx	x.xx
Min, Max	x.x, x.x	x.x, x.x	x.x, x.x	x.x, x.x

Table B.14.2.2.29.1 PDAI – Total Activity Score – Actual Values, Change and Percent Change from Screening and from Baseline (mITT Population)

	400 mg QD (N = n)	400 mg BID (N = n)	600 mg BID (N = n)	Overall (N = n)
WEEK 3 DAY 15 – PERCENT CHANGE FROM SCREENED				
WEEK 3 DAY 15 – CHANGE FROM BASELINE				
WEEK 3 DAY 15 – PERCENT CHANGE FROM BASELINE				
...etc..				

Patients are classified into different dose levels according to the dose they received at each visit.

Program: <program name (date, time)>, Path: <path>

Table B.14.2.2.29.2 PDAI – Total Activity Score – Actual Values, Change and Percent Change from Screening and from Baseline (Completer Population)

Table B.14.2.2.29.3 PDAI – Total Activity Score – Actual Values, Change and Percent Change from Screening and from Baseline (PP Population)

Table B.14.2.2.30.1 PDAI – Total Damage Score – Actual Values and Change from Baseline (mITT Population)

Table B.14.2.2.30.2 PDAI – Total Damage Score – Actual Values and Change from Baseline (Completer Population)

Table B.14.2.2.30.3 PDAI – Total Damage Score – Actual Values and Change from Baseline (PP Population)

Table B.14.2.2.31.1 ABSIS – Skin Involvement Total Score – Actual Values and Change from Baseline (mITT Population)

	400 mg QD (N = n)	400 mg BID (N = n)	600 mg BID (N = n)	Overall (N = n)
WEEK 1 DAY 1 (BASELINE)				
n	x	x	x	x
Mean (SD)	x.xx (x.xxx)	x.xx (x.xxx)	x.xx (x.xxx)	x.xx (x.xxx)
Median	x.xx	x.xx	x.xx	x.xx
Min, Max	x.x, x.x	x.x, x.x	x.x, x.x	x.x, x.x
WEEK 3 DAY 15				
n	x	x	x	x
Mean (SD)	x.xx (x.xxx)	x.xx (x.xxx)	x.xx (x.xxx)	x.xx (x.xxx)
Median	x.xx	x.xx	x.xx	x.xx
Min, Max	x.x, x.x	x.x, x.x	x.x, x.x	x.x, x.x
WEEK 3 DAY 15 – CHANGE FROM BASELINE				
n	x	x	x	x
Mean (SD)	x.xx (x.xxx)	x.xx (x.xxx)	x.xx (x.xxx)	x.xx (x.xxx)
Median	x.xx	x.xx	x.xx	x.xx
Min, Max	x.x, x.x	x.x, x.x	x.x, x.x	x.x, x.x
WEEK 5 DAY 29				
n	x	x	x	x
Mean (SD)	x.xx (x.xxx)	x.xx (x.xxx)	x.xx (x.xxx)	x.xx (x.xxx)
Median	x.xx	x.xx	x.xx	x.xx
Min, Max	x.x, x.x	x.x, x.x	x.x, x.x	x.x, x.x

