Starting Dose	Patient ID	Age/ Gender	Visit	Current PRN Dose	Total Prednisone dosage equivalent (mg/kg)	Weight (kg)	Total Prednisone dosage equivalent (mg)	Reported Medication (R) ATC Level 2 Class Preferred Name/Term (PT)	Start Date (ddMMMyyyy) (Study Day)	Stop Date (ddMMMyyyy) (Study Day)	Indication: AE or MH No.: Dose: (Pred. equiv. dose) Dose unit: Frequency: Route:	Rescue criteria
400 mg QD	xxxxxxx	xx/F	xxx	400 mg QD	xx.xx	xx.x	xx	xxx xxx xxx	ddMMMyyyy ddMMMyyyy		Indication: xxx AE or MH No: AE #1 Dose: 10 (12.5) Dose unit: mg Frequency: xxx Route: xxx	Not applicable
							xx	xxx xxx xxx	ddMMMyyyy Ongoing		Indication: xxx AE or MH No: AE #1 Dose: xx Dose unit: mg Frequency: xxx Route: xxx	Not applicable
							xx	xxx xxx xxx	ddMMMyyyy Ongoing		...etc...	

etc.

F=Female; M=Male

Program: <program name (date, time)>, Path: <path>

Listing B.16.2.6.10 Corticosteroid (CS) Usage on the Day prior to each Visit and CDA/CR Response (ITT Population)

Starting Dose	Patient ID	Age/ Gender	Visit	Current PRN Dose	Previous PRN Dose	Prednisone dosage equivalent (mg/day)*	Prednisone dosage equivalent (mg/kg/day)*	CDA?	CR?
400 mg QD	xxxxxxx	xx/F	SCREENED	---	---	Xx	xx	No	No
			Week 1 DAY 1	400 mg QD	---	Xx	xx	No	No
			WEEK 3 DAY 15	400 mg BID	400 mg QD	Xx	xx	Yes	No
			etc.						

F=Female; M=Male

*For SCREENED and WEEK 1 DAY1: The dosage level on the day of the visit date. For the post-baseline visits: The dosage level at each visit is defined as the dose level the patient is on the day before the visit date.

Program: <program name (date, time)>, Path: <path>

Listing B.16.2.7.1 Pre-treatment Adverse Events (ITT Population)

Starting Dose	Patient ID	Age/ Gender	SOC: System Organ Class PT: Preferred Term V: Verbatim	Start Date (ddMMMyyyy) (Study Day) Stop Date (ddMMMyyyy) (Study Day) or Ongoing Duration (days) (if not ongoing) Pattern of AE (Continuous or Intermittent)	SAE? (Y/N)	CTCAE Grade	Relationship to Study Drug	Details
400 mg QD	xxxxxxx	xx/F	SOC: xxx PT: xxx V: xxx	Start: ddMMMyyyy (Day X) Stop: ddMMMyyyy (Day X) Duration: x days Pattern of AE: xxx	Y	Grade x	xxxx	Action Taken to study drug: xxx Outcome: xxx Has the Cause of the AE been established: Y - xxx Caused study discontinuation?: N or Y Treated for this AE?: Y or N (AE description)

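### Part B by-visit score tables group patients by the dose held at each visit, so the 400 mg qd column keeps mainly adequate responders and flatters that dose

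*SAP*

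**What the plan says.** All references are to the Part B SAP unless stated. The shells for PDAI total activity (Table B.14.2.2.29.1), ABSIS skin involvement (B.14.2.2.31.1) and total anti-DSG (B.14.2.2.49.1) have columns 400 mg QD, 400 mg BID, 600 mg BID and Overall. Each footnote reads "Patients are classified into different dose levels according to the dose they received at each visit".

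The text matches. In Section 5.4.2.4, "percent change from baseline in PDAI total activity, total damage scores will be summarized by dose level and overall, respectively" and "change from baseline in ABQOL and TABQOL scores will also be summarized by dose level and overall in a table"; in Section 5.4.2.5, "Actual values and change from baseline in SNAQ score at each visit will be summarized by dose level and overall". Section 5.4 adds: "For analyses at a particular study drug dose, all patients who received that dose at least once will be included".

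Under Section 2.2, a patient may move from 400 mg qd to 400 mg bid at Week 3 or later, and from 400 mg bid to 600 mg bid at Week 5 or later, for inadequate response. The standard is "Investigator discretion: Generally, clinical response is shown by some improvement seen in first 2 weeks with CDA achieved by the Week 5 visit". Tolerability can prevent the increase.

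Protocol Section 2.1 explains why Part B was opened: "the clinical efficacy of the 400 mg qd dose is being explored to see if lower BTK occupancies will still equate to clinical efficacy".

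Starting dose defines the columns of the disposition, baseline and dose-adjustment tables and orders the listings. No efficacy summary table is planned by starting dose.

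**The concern.** The clinical response that decides whether a patient stays on 400 mg qd is closely tied to the scores these tables summarise. Grouping by dose at the visit therefore lets the outcome help choose the column. After Week 3 the qd column describes mainly patients who did not need escalation, not patients who were given 400 mg qd.

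The higher-dose columns have the opposite fault, because they receive patients selected for doing badly. The 400 mg bid column also mixes those patients with rollovers who started Part B on bid. A reader looking across a row could see an inverse dose-response where none exists. Results from this study are meant to inform confirmatory trials, so a flattering picture of 400 mg qd could carry into later dose choice.

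**Working it through.** **The plan's own figure.** The only planning number is an 80% CI of ±13% for a 50% response rate with 25 patients. It reproduces: 1.2816 × √(0.5 × 0.5 / 25) = 0.128. It is not in dispute; the issue is the structure of the tables.

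**Direction.** Assume no dose effect, and measure improvement in SD units from the mean of all qd starters. Let e be the fraction escalated (the worst responders), c the normal quantile at e, φ the normal density, and ρ the correlation between the response that triggers escalation and the later score. Neither e nor ρ is in the documents. Then

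qd-column mean = ρ × φ(c) / (1 − e).

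- e = 0.3: φ(c)/(1 − e) = 0.50. For ρ from 0.3 to 0.8 the column looks 0.15 to 0.40 SD too good; about 17 of 25 patients remain.
- e = 0.5: 0.80, giving 0.24 to 0.64 SD; about 12 remain.
- e = 0.7: 1.16, giving 0.35 to 0.93 SD; about 7 remain.

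Grouped by starting dose, the mean is 0 in every case.

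**Imperfect escalation.** Suppose half the patients respond poorly, 80% of these and 10% of the rest are escalated, and ρ = 0.5. Those left on qd are 0.5 × 0.2 = 0.10 poor and 0.5 × 0.9 = 0.45 good, so 0.10/0.55 = 18% are poor responders. The column still looks 0.5 × 0.798 × (0.45 − 0.10)/0.55 = 0.25 SD too good. At 60% and 20% the figures are 33% and 0.13 SD.

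**Size on the percentage scale.** Simulation of 300,000 patients with no dose effect. Assumed: mean PDAI change −20%, −35% and −50% at Weeks 3, 5 and 9; SD 35; correlation ρ between successive visits.

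| Scenario (escalated at Week 3 / Week 5) | qd column, Week 9 | All patients | Overstatement |
|---|---|---|---|
| ρ 0.7; worst 30% / 50% | −70.7 | −50.1 | 70.7/50.1 = 1.41, so 41% |
| ρ 0.7; worst 30% / 39% | −67 | −50 | 34% |
| ρ 0.4; worst 30% / 50% | −61.7 | −50 | 23% |
| ρ 0.7; worst 10% / 20% | −59 | −50 | 18% |
| ρ 0.7; 60% of those in the worst 30% / 50%, change floored at −100% | −59.6 | −48.8 | 22% |
| ρ 0.4; same | −54.4 | −48.8 | 11% |

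The 50% is the planning response rate. The 39% is 1 − 0.61, from the 11 of 18 responders reported in the protocol for Part A, whose patients started on 400 mg bid. In the first row the 400 mg bid and 600 mg bid columns show −40.4 and −24.7, and 45% of starters remain in the qd column.

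**The escalation visit.** The shells do not say whether the dose at a visit means before or after a change made there. The sample row of Listing B.16.2.6.10, "WEEK 3 DAY 15 400 mg BID 400 mg QD", gives the new dose as current and qd as previous. If the tables used that current dose, a poor Week 3 score earned on qd would be printed under bid.

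**The case against.** Several points on the other side stand.

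- A reader might infer that the qd column holds only patients doing well. It does not follow. Escalation is permitted rather than required, rests on the investigator's judgement and can be blocked by tolerability. The supportable word is mainly.
- A reader might see a contradiction with the at-least-once rule in Section 5.4. None is shown: that rule can set who may contribute to a dose column and the footnote which visits they contribute. Equally, it does not remove the selection.
- ABQOL, TABQOL and SNAQ have no shell or footnote, so the rule is inferred for them. The corticosteroid tables B.14.2.2.23 to .28 also have dose columns, but their footnotes appear to define the steroid dose, so the point is not extended to them.
- Misattribution at Week 3 rests on one dummy listing row, and Section 6 says shells may be adjusted. The CDA tables use the dose received before response. This is an ambiguity, not an established error.
- The largest simulated figures assume strict escalation on ranked PDAI change and allow improvements beyond −100%. Relaxing both roughly halves the overstatement.
- The tables are secondary and descriptive, no hypothesis test is planned, and per-patient PDAI plots show dose over time.

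The Overall column is a partial answer. It is free of this selection, and new Part B patients all start on qd. However, it pools them with 400 mg bid starters, whose number is not given.

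**Conclusion.** The point holds. As specified, membership of the dose columns from Week 3 depends on response. This favours 400 mg qd and disfavours the higher doses even if dose makes no difference, and no planned efficacy summary by starting dose offsets it.

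The direction follows from the escalation rule and the footnote, provided that early response and later score are positively correlated. The size cannot be fixed from the documents. The scenarios give an overstatement of roughly 11% to 41% in the Week 9 qd mean; these are not bounds, and weaker correlation or looser escalation would give less.

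Confidence is firmest for PDAI, ABSIS and anti-DSG. Sections 3.2.8 (Patients from Part A) and 3.3 (Treatment Groups) are in the contents list, but their text was not available, so any further grouping rule there could not be checked. Because the tables are descriptive, this should be corrected before they are interpreted by dose; it does not undermine the primary CDA analysis.

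**What to change.** 1. In the PDAI, ABSIS, ABQOL, TABQOL, SNAQ and anti-DSG by-visit tables, use the columns Starting dose 400 mg QD, Starting dose 400 mg BID and Overall. Keep each patient in the starting-dose column at every visit.
2. Keep dose-at-visit columns, if wanted, as supplementary tables with a footnote that membership depends on response and the columns are not comparable.
3. State that a score at an escalation visit is attributed to the dose taken before that visit.
4. If a summary of 400 mg qd alone is wanted, limit it to the Week 3 assessment by pre-visit dose. A row pooling each patient's last assessment on qd would mix Week 3 values from escalated patients with later values from the rest, confounding duration with response.

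The cost is SAP and shell wording and a rerun by a variable the SAP already uses; trial conduct does not change. The downside is that the starting-dose column estimates the strategy of starting on qd and escalating as needed, not the effect of staying on qd.
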